			Cycle 0 (6 Weeks)			Cycle 1 (4 Weeks)		Cycle 2 (4 Weeks)		Cycle 3+ ^a (4 Weeks)		EOT ^b	Follow-up ^c		
	Screening 1	Screening 2	Day 1	Day 15	Day 29	Day 1	Day 15	Day 1	Day 15	Day 1	Day 15		N/A	30 Days	90 Days
Assessment/Procedure	Days -28 to -1	Days -28 to -1	N/A	±7 Days										±3 Days	±7 Days
Written Informed Consent	X ^d														
Medical History	X														
Physical Exam ^e	X		X	X	X	X	X	X	X	X	X	X	X	X	X
Vital Signs ^f	X		X ^g	X ^g	X ^g	X ^h	X ^o	X ^o	X ^o	X ^o	X ^o	X	X	X	X
ECOG PS	X		X	X	X	X	X	X	X	X	X	X	X	X	X
Adverse Event Evaluation	X		X	X	X	X	X	X	X	X	X	X	X	X	X
Concomitant medications	X		X	X	X	X	X	X	X	X	X	X	X	X	X
CBC w/Diff ⁱ	X		X	X	X	X	X	X	X	X	X	X	X	X	X
Chemistry Panel ^j	X		X	X	X	X	X	X	X	X	X	X	X	X	X
Beta hCG ^k	X		X			X		X		X		X			
Thyroid Function ^l	X					X		X		X		X			
Urinalysis ^m	X		X			X		X		X		X	X	X	X
Coagulation ⁿ	X														
Hepatitis/HIV Screening ^o	X														
ECG ^p	X														
Tumor Imaging ^q	X ^r					X ^s				X ^s					
RECIST ^t	X					X				X					
Biopsy ^u	X ^v	X ^w			X ^x				X ^y						
CA125			X			X		X		X		X		X	
Research Blood ^z			X			X		X		X ^{aa}					X
AVB-S6-500 dosing ^{bb}			X	X	X	X	X	X	X	X	X	X			
Durvalumab dosing ^{cc}						X		X		X					

^a The procedures/assessments including treatment will continue until intolerable toxicity or confirmed progression.

^b End of treatment (EOT) is defined as the last visit where the decision is made to discontinue protocol directed treatment, including confirmed progression of disease. All required procedure may be completed within ± 7 days of the end of treatment visit. Repeat disease assessment is not required if performed within 35 days prior to the EOT visit.

^c For subjects who end treatment due to progression, follow-up visits will occur every 6 weeks for at least 90 days or until initiation of subsequent treatment or alternative trial. For subjects who are no longer receiving study drug(s) but have not had confirmed progression, follow-up with clinical and laboratory evaluation will occur every 6 weeks with imaging assessment every 12 weeks (unless more frequent assessment is clinically indicated) for at least 90 days or until progression, whichever occurs later. All patients should have further chemistry profiles performed at 30 days (±3 days) and 90 days (±1 week) after permanent discontinuation of IP. All patients will be followed for survival. Patients who decline to return to the site for evaluations will be offered follow-up by phone every 6 months as an alternative.

^d Informed consent of study procedures and pretreatment tumor biopsy sample may be obtained prior to the 28-day screening window, if necessary, in order to permit tumor biopsy sample acquisition and analysis prior to randomization. If laboratory or imaging procedures were performed for alternate reasons prior to signing consent,

these can be used for screening purposes with consent of the patient. However, all screening laboratory and imaging results must have been obtained within 28 days of randomization.

^e Full physical exam will be performed at screening, with targeted physical exam at all other time points. Body weight is recorded at each visit. Height to be performed at screening only.

^f Routine vital signs to be performed at each visit, and these should occur prior to infusion on treatment days.

^g During administration of monotherapy AVB-S6-500: BP and pulse will be collected from patients prior to the beginning of the infusion (measured once from approximately 30 minutes before up to 0 minutes [i.e., the beginning of the infusion]), approximately 15 minutes during the infusion (halfway through infusion), and at the end of the infusion (approximately 30 minutes \pm 5 minutes). If the infusion takes longer than 30 minutes, then BP and pulse measurements should follow the principles as described above or be taken more frequently if clinically indicated. A 1-hour observation period is recommended after the first infusion of AVB-S6-500.

^h During administration of combination therapy: BP and pulse will be collected from patients prior to the beginning of the infusion (measured once from approximately 30 minutes before up to 0 minutes [i.e., the beginning of the infusion]), approximately 30 minutes during the infusion (halfway through infusion), and at the end of the infusion (approximately 60 minutes \pm 5 minutes). If the infusion takes longer than 60 minutes, then BP and pulse measurements should follow the principles as described above or be taken more frequently if clinically indicated. A 1-hour observation period is recommended after the first dose of combination therapy.

ⁱ May be performed more frequently than noted in the schedule if clinically indicated. CBC with differential includes: basophils, eosinophils, hematocrit, hemoglobin, lymphocytes, mean corpuscular hemoglobin, mean corpuscular hemoglobin concentration, mean corpuscular volume, monocytes, neutrophils, platelet count, red blood cell count, and total white cell count.

^j May be performed more frequently than noted in the schedule if clinically indicated. Chemistry Panel includes: albumin, alkaline phosphatase, alanine aminotransferase, amylase, aspartate aminotransferase, bicarbonate, calcium, chloride, creatinine, gamma glutamyltransferase, glucose, lactate dehydrogenase, lipase, magnesium, potassium, sodium, total bilirubin total protein, BUN, and uric acid. If total bilirubin is $\geq 2 \times$ ULN (and no evidence of Gilbert's syndrome) then fractionate into direct and indirect bilirubin. Amylase and lipase are to be performed at screening, Day 1 of each cycle, and at EOT. It is preferable that both amylase and lipase parameters are assessed. For sites where only 1 of these parameters is routinely measured then either lipase or amylase is acceptable. Bicarbonate, chloride, creatinine clearance, and magnesium testing are to be performed at screening, on Day 0 (if required), and if clinically indicated. If a patient shows an AST or ALT $\geq 3 \times$ ULN together with total bilirubin $\geq 2 \times$ ULN, refer to **Section 6.3** for further instructions on cases of increases in liver biochemistry and evaluation of Hy's Law. Gamma glutamyltransferase may be included at any time if clinically indicated.

^v Biopsy can be newly acquired or archival ≤ 3 years old. If subjects are not required to have a diagnostic biopsy (i.e. tumor recurrence/progression has been already histologically confirmed), tissue acquisition will occur during a research-only biopsy procedure. Refer to **Section 6.6.2** for details regarding tumor sample.

^w If subjects are not required to have a diagnostic biopsy (i.e. tumor recurrence/progression has been already histologically confirmed), tissue acquisition will occur during a research-only biopsy procedure. Refer to **Section 6.6.2** for details regarding tumor sample.

^x To occur immediately prior to initiation of combination therapy. Refer to **Section 6.6.2** for details regarding tumor sample.

^y To occur immediately prior to initiation of Cycle 3 where possible. Refer to **Section 6.6.2** for details regarding tumor sample.

^z Samples will be taken within 45 minutes before dosing. Refer to **Section 6.6.1**. A blood sample will be collected and processed for serum at the 90-day follow up visit to analyze for the presence of anti-drug antibodies for AVB-S6-500.

^{aa} Cycles 3 and 4 only.

^{bb} Refer to **Section 5.2**.

^{cc} Refer to **Section 5.1**.

6.6 BIOLOGICAL SAMPLING PROCEDURES

6.6.1 RESEARCH BLOOD

A pharmacokinetics/pharmacodynamics (AVB-S6-500 plasma concentration/GAS6 suppression) model was developed from non-human primate (monkey) data, scaled to humans, and used to predict human AVB-S6-500 exposure and GAS6 suppression (refer to AVB-S6-500 Investigator Brochure for more complete details). In healthy volunteer studies, GAS6 was demonstrated to be suppressed for at least 3 weeks post-dose administration. Therefore, in the current study we will collect blood to evaluate GAS6 levels as a relevant biomarker at cycles 1 and 2, immediately prior to dose administration.

Blood will be collected on the days noted in the Schedules of Assessments in **Section 6.5**. Sample collection specifics are detailed below.

Table 9. Detailed Research Blood Collection Schedule

Phase of Study	Safety Lead-in		Phase II: Durvalumab		Phase II: AVB-S6-500	
	Serum	Plasma/ PBMC	Serum	Plasma/ PBMC	Serum	Plasma/ PBMC
Time point						
Cycle 0 Day 1: Pre-treatment		N/A		X	X	X
Cycle 1 Day 1: Pre-treatment	X	X	X	X	X	X
Cycle 1 Day 1: 1 hour after treatment	X					
Cycle 1 Day 1: 4 hours after treatment	X					
Cycle 2 Day 1: Pre-treatment	X	X	X	X	X	X
Cycle 3 Day 1: Pre-treatment		X		X		X
Cycle 4 Day 1: Pre-treatment		X		X		X
90-day Follow-Up	X		X ^a		X	

^a Only for patients who have received at least one dose of AVB-S6-500.

Serum fractions will be isolated from blood samples collected in EDTA-free tubes and will be used to measure 1) PK: AVB-S6-500 concentrations in serum, 2) Pharmacodynamics: GAS6 suppression, which will be analyzed by Altasciences, and 3) Anti-drug Antibody (ADA): immunogenicity of AVB-S6-500, which will be analyzed by Charles River Labs. Blood will be collected and processed for serum for analysis of AVB-S6-500 ADA at the 90 day Follow Up visit.

Plasma and PBMCs will be extracted from blood samples collected in EDTA-containing tubes and will be used for planned translational analysis, including gene expression analysis, functional proteomics, and immune profiling using a variety of complementary platforms. It is important to note that assays available for analysis of trial specimens are continuously evolving, thus the final method/platform used will be selected by primary investigators and translational collaborators at the time of specimen analysis.

6.6.2 TUMOR BIOPSIES

Pre- and on-treatment biopsies will be performed as part of this clinical investigation. To avoid putting patients in undue risk, procedures more invasive than a core biopsy will not be used. Pretreatment biopsies will be collected prior to the first dose of study drug regimen. On-treatment biopsies include sampling after monotherapy treatment and then after combination treatment with Durvalumab and AVB-

S6-500 when there is a lesion amenable to biopsy as assessed by imaging study by MDACC Radiologist. The time points for each Phase and Arm are noted in the Schedules of Assessments in **Section 6.5**.

When possible, on-treatment biopsies will be obtained from the same area of tumor as the pre-treatment biopsy.

At all biopsy time points and when deemed clinically safe, up to 10 core biopsies will be collected by Radiology faculty through an image-guided procedure. When feasible and depending on the tumor volume, 1-3 cores will be processed as formalin-fixed, paraffin-embedded blocks (FFPE) and 1-3 cores will be flash frozen, and remaining cores will be kept fresh in media. In cases where only limited amounts of tumor can be obtained, the FFPE samples will be prioritized. Samples will be collected, labeled, processed, and stored by the MDACC Gynecologic Oncology Tumor Bank. Sample identification and associated collection data will be entered into a secure database.

Translational studies including tumor immune and gene expression profiling will be performed with collaborators at MD Anderson group and Discovery Life Sciences (DLS). This assessment may include, but is not limited to, fresh flow cytometry, tissue cyTOF, and multiplex immunofluorescence. Exploratory analyses may include sequencing platforms and, given that assays for these evaluations are rapidly evolving in the laboratories at MDACC, other assays will be performed with the current state of the art technology available at the time of analysis. Aliquots may be stored and used for exploratory and future translational immunology research.

6.6.3 WITHDRAWAL OF INFORMED CONSENT FOR DONATED BIOLOGICAL SAMPLES

If a patient withdraws consent to the use of donated samples, the samples will be disposed of/destroyed, and the action documented. However, any data that was previously generated from the sample will be retained. Such subjects may still continue with the therapeutic portion of the investigation.

The Principal Investigator:

- Ensures that biological samples from that patient, if stored at the study site, are immediately identified, disposed of /destroyed, and the action documented
- Ensures the laboratory(ies) holding the samples is/are informed about the withdrawn consent immediately and that samples are disposed/destroyed, the action documented and the signed document returned to the study site
- Ensures that the patient is informed about the sample disposal

7. DISEASE EVALUATION AND METHODS

7.1 MODIFIED RECIST V1.1

The response to immunotherapy may differ from the typical responses observed with cytotoxic chemotherapy. These difference include the following [59], [60]:

- Response to immunotherapy may be delayed,
- Response to immunotherapy may occur after PD by conventional criteria,
- The appearance of new lesions may not represent PD with immunotherapy, and
- SD while on immunotherapy may be durable and represent clinical benefit.

Based on the above-described unique response to immunotherapy and based on guidelines from regulatory agencies, e.g., European Medicines Agency's "Guideline on the evaluation of anticancer medicinal products in man" (EMA/CHMP/205/95/Rev.4) for immune modulating anticancer compounds, we will implement the following modifications in addition to standard RECIST 1.1 criteria.

- RECIST will be modified so that PD must be confirmed at the next scheduled visit, preferably, and no earlier than 5 weeks after the initial assessment of PD in the absence of clinically significant deterioration. Treatment with durvalumab and AVB-S6-500 would continue between the initial assessment of progression and confirmation for progression.
- In addition, patients may continue to receive durvalumab and AVB-S6-500 beyond confirmed PD in the absence of clinically significant deterioration and if investigators consider that patients continue to receive benefit from treatment.

Modification of RECIST as described may discourage the early discontinuation of durvalumab and AVB-S6-500 and provide a more complete evaluation of its antitumor activity than would be seen with conventional response criteria. Nonetheless, the efficacy analysis will be conducted by programmatically deriving each efficacy endpoint based on RECIST 1.1 criteria.

Of note, clinically significant deterioration is considered to be a rapid tumor progression that necessitates treatment with anticancer therapy other than durvalumab or with symptomatic progression that requires urgent medical intervention (e.g., central nervous system metastasis, respiratory failure due to tumor compression, spinal cord compression).

7.1.1 PHYSICAL EXAMINATION

Lesions detected by physical examination will only be considered measurable if superficial, e.g., skin nodules and palpable lymph nodes. Documentation by color photography including ruler is recommended for estimating the size of skin lesions.

7.1.2 CT SCAN WITH CONTRAST OF THE CHEST, ABDOMEN, AND PELVIS

CT scans should be performed with contiguous cuts in slice thickness of 5 mm or less. Spiral CT should be performed using a 5-mm contiguous reconstruction algorithm.

7.1.3 MRI SCANS

MRI of the abdomen and pelvis is acceptable for measurement of lesions provided that the same anatomical plane is used for serial assessments. If possible, the same imaging device should be used for serial evaluations. In case of MRI, measurements will be preferably performed in the axial (transverse) plane on contrast-enhanced T1-weight

7.1.4 MEASURABILITY OF TUMOR LESIONS

Tumor lesions will be categorized as follows.

7.1.4.1 MEASURABLE LESIONS

Measurable lesions must be accurately measured in at least one dimension (longest diameter in the plane of measurement is to be recorded) with a minimum size of:

- 10 mm by CT scan (irrespective of scanner type) and MRI (no less than double the slice thickness and a minimum of 10 mm).
- 10 mm caliper measurement by clinical exam (when superficial).

Malignant lymph nodes are considered pathologically enlarged and measurable, a lymph node must be \geq 15 mm in short axis when assessed by CT scan (CT scan slice thickness recommended to be no greater than 5 mm).

7.1.4.2 NONMEASURABLE LESIONS

Nonmeasurable lesions are defined as all other lesions (or sites of disease), including small lesions (longest diameter < 10 mm or pathological lymph nodes with ≥ 10 to < 15 mm short axis). Lesions considered truly nonmeasurable include the following: leptomeningeal disease, ascites, pleural/pericardial effusion, lymphangitic involvement of skin or lung, abdominal masses/abdominal or organomegaly identified by physical exam that is not measurable by reproducible imaging techniques.

7.1.4.3 TARGET LESIONS

All lesions up to a maximum of 5 lesions total (and a maximum of 2 lesions per organ) representative of all involved organs should be identified as target lesions. It may be the case that, on occasion, the largest lesion does not lend itself to reproducible measurement in which circumstance the next largest lesion which can be measured reproducibly should be selected.

7.1.4.4 NON-TARGET LESIONS

It is possible to record multiple nontarget lesions involving the same organ as a single item on the case record form (e.g., “multiple enlarged pelvic lymph nodes” or “multiple liver metastases”). Patients who have disease control following completion of 12 months of treatment or patients who are withdrawn from durvalumab + AVB-S6-500 treatment for reasons other than confirmed PD will continue to have objective tumor assessments (see Schedule of Assessments).

7.2 RESPONSE CRITERIA

7.2.1 EVALUATION OF TARGET LESIONS

- **Complete Response** - Disappearance of all target lesions. Any pathological lymph nodes (whether target or non-target) must have reduction in short axis to < 10 mm (the sum may not be “0” if there are target nodes).
- **Partial Response** - At least a 30% decrease in the sum of the diameters of target lesions, taking as reference the baseline sum diameters.
- **Progressive Disease** - At least a 20% increase in the sum of diameters of target lesions, taking as reference the smallest sum on study (this includes the baseline sum if that is the smallest on study). In addition to the relative increase of 20%, the sum must also demonstrate an absolute increase of at least 5 mm. (Note: the appearance of one or more new lesions is also considered progression.)
- **Stable Disease** - Neither sufficient shrinkage to qualify for PR nor sufficient increase to qualify for PD, taking as reference the smallest sum of diameters while on study.

7.2.2 EVALUATION OF NON-TARGET LESIONS

- **Complete Response** - Disappearance of all non-target lesions and normalization of tumor marker level. All lymph nodes must be non-pathological in size (< 10 mm short axis).
- **Non-complete response/Non-progressive disease** - Persistence of 1 or more non-target lesion(s) and/or maintenance of tumor marker level above the normal limits.
- **Progressive Disease** - Unequivocal progression of existing non-target lesions will be defined as the overall level of substantial worsening in non-target disease such that, even in presence of SD or PR in target disease, the overall tumor burden has increased sufficiently to merit discontinuation of therapy. In the absence of measurable disease, change in non-measurable disease comparable in magnitude to the increase that would be required to declare PD for

measurable disease. Examples include an increase in a pleural effusion from ‘trace’ to ‘large,’ an increase in lymphangitic disease from localized to widespread.

7.2.3 APPEARANCE OF NEW LESIONS

The appearance of new lesions is considered PD according to RECIST v 1.1 guidelines. However, considering the unique response kinetics that have been observed with immunotherapy, new lesions may not represent true disease progression. In the absence of rapid clinical deterioration, subjects may continue to receive the study regimen if investigators consider that subjects continue to benefit from treatment. A confirmatory radiologic assessment should be performed at least 5 weeks from the original study suggesting PD.

7.2.4 EVALUATION OF OVERALL RESPONSE WITH MODIFICATIONS

Confirmation of CR, PR, as well as PD is required by a repeat, consecutive assessment no less than 5 weeks from the date of first documentation. Treatment with study regimen will continue between the initial assessment of PD and confirmation for PD. If PD is confirmed by the second confirmatory scan, the associated time of progression will be reported as that of the initial imaging study revealing progression. In the absence of clinical deterioration, such modifications to the RECIST criteria may discourage the early discontinuation of the study regimens and provide a more complete evaluation of its antitumor activity than would be seen with conventional response criteria.

Table 10 provides overall responses for all possible combinations of tumor responses in target and non-target lesions with or without the appearance of new lesions.

Table 10. Overall Responses for All Possible Combinations of Tumor Responses

Target Lesions	Non-target Lesions	New Lesions	Overall Response
Complete response	Complete response (or no non-target lesion)	No	Complete response
Complete response	Not evaluable ^a	No	Partial response
Complete response	Non-complete response/non-progressive	No	Partial response
Partial response	Non-progressive and non-evaluable ^a	No	Partial response
Stable disease	Non-progressive and non-evaluable ^a	No	Stable disease
Not all evaluated	Non-progressive	No	Not evaluable
Progressive disease	Any	Yes/No	Progressive disease ^b
Any	Progressive disease	Yes/No	Progressive disease ^b
Any	Any	Yes	Progressive disease ^b

^a Not evaluable is defined as either when no or only a subset of lesion measurements are made at an assessment

^b Disease progression requires confirmatory radiologic assessment

Confirmation of progression guidelines are set for the following reasons:

- for patient management and treatment decisions and
- in the absence of significant clinical deterioration, to promote the collection of additional scans after the first radiologic RECIST 1.1 assessment of progressive disease (PD) in order to distinguish pseudoprogression from true radiologic progression, also known as RECIST 1.1 modified for confirmation of progression.

Confirmed objective disease progression refers to either of the following scenarios: 1. clinical progression/deterioration followed by a radiologic verification scan (PD by RECIST 1.1); or 2. in the absence of significant clinical deterioration, radiologic PD by RECIST 1.1 followed by a second radiologic confirmation scan with PD assessed according to the specific confirmation of progression criteria listed below. RECIST 1.1 modified for confirmation of progression refers to the second scenario above. The confirmatory scan should occur preferably at the next scheduled imaging visit and no earlier than 5 weeks following the date of the immediate prior assessment of RECIST 1.1 PD.

Immediate prior radiologic progression would be considered confirmed if any the following criteria are met in the confirmatory scan:

- $\geq 20\%$ increase in the sum diameters of target lesions (TLs) compared with the nadir at 2 consecutive visits, with an absolute increase of at least 5 mm in sum of diameters compared to nadir,
- and/or significant progression (worsening) of non-target lesions (NTLs) and/or of pre-existing new lesions at the confirmatory scan time-point compared with the immediate prior time-point (Note: Pre-existing new lesions are evaluated as NTLs at the confirmatory scan time-point), and/or
- additional new unequivocal lesions at the confirmatory scan time-point.

To have confirmed objective disease progression, there should be two consecutive assessments meeting the PD definition: the first PD by RECIST 1.1 and the second PD using the confirmation of progression criteria (above). If the first assessment fulfilling the PD definition by RECIST 1.1 is not confirmed, continue with assessments until the next PD by RECIST 1.1, which in turn will need its own immediate subsequent confirmation scan. In the absence of significant clinical deterioration, treatment with study drug may continue between the initial assessment of progression and the scan to confirm progression.

If the confirmation scan confirms progression, then the date of the prior scan with PD should be declared as the date of progression.

If progression is not confirmed, in the absence of significant clinical deterioration, then the patient should continue study drug and on-treatment assessments until the next PD which will also require a follow-up confirmation scan. **If the first PD is not confirmed by the immediate next scan, then the Investigator should change the PD assessment of the first scan.**

If a patient discontinues treatment (and/or receives a subsequent anticancer therapy) prior to radiologic progression, then the patient should still continue to be followed until confirmed objective disease progression.

Following confirmed progression, patients should continue to be followed up for survival as outlined in the follow-up schedules of assessments.

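### Changing the first PD reading when the next scan does not confirm it conflicts with deriving efficacy endpoints by RECIST 1.1

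*Combined protocol and SAP*

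**What the plan says.** Section 7.1 introduces modified rules under which PD needs confirmation and treatment may continue meanwhile. It then separates these from the analysis: "the efficacy analysis will be conducted by programmatically deriving each efficacy endpoint based on RECIST 1.1 criteria".

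Section 7.2.4 gives two reasons for confirming progression. The first is "for patient management and treatment decisions". The second is to collect further scans "in order to distinguish pseudoprogression from true radiologic progression". For an unconfirmed PD it first gives a rule that edits nothing: "If the first assessment fulfilling the PD definition by RECIST 1.1 is not confirmed, continue with assessments until the next PD by RECIST 1.1". A little further on, in bold, it adds that when the next scan does not confirm the first PD, "then the Investigator should change the PD assessment of the first scan".

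Section 2.2 names RECIST 1.1 in the objective for irPFS and OS. Section 9.2 takes the definition of response from Section 7.2 and runs irPFS to the initial radiologic evidence of PD, again citing Section 7.2. Nowhere do the documents say that the original reading is kept, that confirmation status is a separate variable, or that an independent reader holds the first assessment.

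**The concern.** A time-point assessment should record what was seen at that time point. Here the entry for one scan is rewritten once the next is known, so a recorded outcome depends on a later outcome. The rewriting also runs one way: PD can be taken out, and no matching instruction puts a PD in.

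Section 7.1 promises a RECIST 1.1 derivation. If its input is the edited assessment, the RECIST 1.1 PD may no longer be there to find. A patient who progressed by RECIST 1.1 could then appear progression-free, or be counted as a responder after a later shrinkage. At stake is whether RECIST 1.1 best response, ORR and progression time can be reproduced from the trial data.

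**Working it through.** No figure in the plan bears directly on this point, so there is none to reproduce. The check compares the rules and then applies them to two constructed patients.

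**1. What counts as PD.** Under Sections 7.2.1 to 7.2.3 and Table 10, overall PD arises by three routes:
- Target lesions: an increase of at least 20% over the smallest sum, and at least 5 mm.
- Non-target lesions: "Unequivocal progression of existing non-target lesions will be defined as the overall level of substantial worsening".
- New lesions: "The appearance of new lesions is considered PD according to RECIST v 1.1 guidelines".

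**2. What the edit puts at risk, by route.**
- Target sums: the input is a set of diameters. The instruction changes the assessment and says nothing about the diameters, so PD can be recomputed if they are kept.
- New lesions: the input is the lesion entry. PD can be recomputed if the entry stays, but not if it is altered to match the changed assessment.
- Non-target progression: the input is the investigator's judgment. Once that is changed, the documents describe nothing else from which to derive it.

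**3. Constructed patient A, target lesions.** Assumed sums are 50, 62, 48, 34 and 34 mm at baseline and weeks 8, 16, 24 and 32.
- Week 8: (62 − 50)/50 = +24%, and +12 mm. This is PD.
- Week 16: (48 − 50)/50 = −4%. PD is not confirmed, so the week 8 assessment is to be changed.
- Weeks 24 and 32: (34 − 50)/50 = −32% from baseline at both. This passes the 30% threshold for PR, and the scans are 8 weeks apart against a 5-week minimum, so PR is confirmed.

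With the week 8 reading kept, the patient progressed at week 8 by RECIST 1.1. With it changed, the patient is a responder with no progression through week 32. This assumes that a RECIST 1.1 best response closes at the first PD. Section 7.1 points that way, since it lists response after conventional PD as a way in which immunotherapy differs.

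**4. Constructed patient B, new lesion.** Target sums are flat. One new lesion appears at week 8 and is unchanged at week 16, with no others. Table 10 gives PD at week 8. The Section 7.2.4 confirmation criteria at week 16 are:
- target increase of at least 20%: no;
- significant worsening of non-target or pre-existing new lesions against the prior scan: no;
- additional new lesions: no.

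PD is therefore unconfirmed and the week 8 reading is to be changed, although the lesion is still present. So the instruction reaches beyond pseudoprogression that has resolved.

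**5. Effect on each endpoint.** Where irPFS requires confirmed PD, an unconfirmed PD is not an event whether or not its label is edited, and a confirmed PD is dated to the first PD scan. That endpoint hardly moves. RECIST 1.1 best response, ORR and progression time do move, as patients A and B show.

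**6. Scale.** The documents give no frequency of unconfirmed PD. If the efficacy set holds five patients (assumed from Section 3.1), one reclassified patient changes ORR by 1/5 = 20 percentage points. If it held 15, the dose-finding maximum in step 3 of Section 9, the change would be 1/15 = 6.7 points. Section 1.6.1 puts checkpoint monotherapy response at about 10-15%.

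**The case against.** The strongest reply has four parts.

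First, the instruction changes an assessment, not the measurements, and a programmatic derivation can be read as working from lesion data. This stands for target sums, and for new lesions if their entries stay. It does not cover non-target progression, and no text promises that the lesion records will be left alone. A reader might infer that the RECIST 1.1 data are destroyed outright. The documents do not show that: they do not describe the case report form fields or audit trail for tumor readings.

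Second, the only progression endpoint listed is irPFS, and Section 7.2.4 requires PD to be confirmed. On that reading the edit leaves irPFS almost unchanged. This stands. A reader might infer that irPFS is lengthened generally, but that would follow only if irPFS were dated from the first unconfirmed PD.

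Third, a response after an unconfirmed PD would count under the modified criteria even without the edit. This also stands. It shows that the plan never settles whether RECIST 1.1 or the modified criteria govern ORR and irPFS, and deleting one sentence would not settle it.

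Fourth, a reader might set one 8-week imaging interval against a median PFS of about 3 months, 8/13 = 0.61, and infer an effect of about 60% of the median. That divides one patient's shift by a group median, and Section 1.6.1 reports that median from prior trials of other therapies. It is not an estimate of bias.

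**Conclusion.** The conflict is real and nothing else in the documents resolves it. Followed as written, Section 7.2.4 makes an outcome-dependent, one-directional change to data that Section 7.1 needs for a RECIST 1.1 derivation. The risk is clearest for non-target progression, conditional for new lesions, and avoidable for target sums. It bears on RECIST 1.1 best response, ORR and any RECIST 1.1 progression time, and little on irPFS based on confirmed PD.

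No percentage effect on median PFS can be claimed. The 20-point ORR figure is what one reclassified patient would mean in an assumed set of five; it is not an expected bias. Practical impact is limited: toxicity is the primary objective, efficacy is secondary, enrollment ended after the fifth evaluable subject, and Section 9 states that the phase II design no longer applies, so no efficacy decision rule depends on this. It is still worth correcting, because ORR and irPFS remain stated objectives and in so few patients each reading counts.

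**What to change.** Reconcile Section 7.2.4 with Section 7.1:
- Remove the instruction to change the first-scan reading.
- Keep every time-point assessment and lesion record as first entered, and restore from source any already changed.
- Add one field: PD confirmed at next scan, yes / no / not done.
- Derive the RECIST 1.1 endpoints and the confirmed-PD (irPFS) endpoints from the same unedited data.
- State in Section 9.2 which criteria govern ORR and which govern irPFS.

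The cost is one deleted sentence, one added field, a short clarification in Section 9.2, and a check of source records for the few patients treated. This concerns recording and analysis only and leaves the rules on continuing treatment untouched.
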